8.4. Follow-up Procedures

Results from surgical intervention and/or any additional follow-up resulting from biopsy(ies) (e.g., breast ultrasound or magnetic resonance imaging [MRI]) will be considered in determining truth of cancer status.

No additional follow-up appointments will be required for subjects that have completed biopsy/surgical intervention with positive findings or documented histologic concordance with imaging.

8.5. Incidental Findings

If any unexpected atypical or abnormal findings unrelated to the study aims (breast cancer identification) are identified during this study that may incidentally indicate other diseases or other unknown conditions, these cases will be reported to the Site Principal Investigator. If the Site Principal Investigator determines that these findings are medically significant in his or her medical judgment, he or she will notify the subject and refer her for further follow-up outside of this study according to the standard of care at the investigational site. Follow-up for incidental findings is not required by this study, but relevant images and data resulting from examinations related to incidental findings may be provided to the Sponsor, at the discretion of the Principal Investigator, if determined to be relevant to study conduct or integrity of study results.

8.6. Withdrawal and Discontinuation Criteria

8.6.1. Subject Withdrawal Rules

The subject's medical care shall take precedence over any research imaging or other procedures associated with the study. If it is discovered during the study (any time after consent has been signed or study procedures have begun) that any study procedure will negatively impact required clinical care, the subject shall be withdrawn from the study.

Each subject is free to withdraw from the study at any time. Investigator(s) also have the right to withdraw subjects from the study in the event of illness, AEs, SAEs, or other reasons concerning the health or well-being of the subject, or in the case of lack of cooperation.

If a subject withdraws (or is withdrawn), all efforts will be made to complete and report the observations up to the time of withdrawal. A complete final evaluation at the time of the subject's withdrawal should be made and an explanation given on the CRF given as to why the subject is withdrawing or being withdrawn from the study. If the reason for withdrawal is a clinical AE or SAE, monitoring will continue until the outcome is evident. The specific event or test result(s) must be recorded on the CRF.

In the event the subject experiences pain, undue discomfort, or destabilizing vital signs that is observed by visual inspection or via monitoring equipment, or requests to discontinue study procedures, the study procedures will be stopped immediately, and the appropriate response will be taken according to the standard of care at the investigational site.

A subject may withdraw from study participation at any time, for any reason without consequence. The study staff may withdraw a subject at any time for any reason. There shall be no negative repercussions to the subject. The reasons for withdrawal and discontinuation for any subject shall be recorded. These will be reported to the Sponsor. The EC/IRB should be notified per their notification of subject withdrawal policy.

As described in Section 8.3 Biopsy Procedures, subjects with initial benign/negative histopathology results that are discordant with imaging findings will be withdrawn from this study if no rebiopsy or histopathology occurs, or if histopathology remains discordant with imaging findings following rebiopsy.

Subjects withdrawn after consent is signed will be counted as enrolled subjects up until the time of withdrawal, and will be considered in reporting total enrolled subjects in this study per the populations defined in Section 10.1.2. - Study Populations.

9. TRAINING PLAN

9.1. Training Plan for Research Device/Product

Training will be provided to study staff on the use of device system(s), as needed. Study staff that will be operating the device(s) during subject procedures may be required to receive additional training above that is required by other study staff. The Sponsor will provide instructions for use of the device and, as necessary, subsequent training, at the Sponsor's discretion or upon request by the site.

9.2. Training Plan for Protocol

Study staff will be trained on the study protocol and study procedures, including completion of Informed Consent Forms (ICFs), Case Report Forms (CRFs), and other study documentation.

Training will also be provided to ensure appropriate storage and handling of images and data. All study staff will be required to be trained on Good Clinical Practice (GCP) guidelines per ISO 14155: 2011.

A record of all formal training attendance and date conducted will be stored in the Site Regulatory Binder and provided to the Sponsor for inclusion in the Sponsor's Clinical History File (CHF).

9.3. Reader Training

All study staff assessing images for this study will be qualified radiologists at the investigational site(s), and reads will be performed according to the standard of care at the investigational site. All readers will be trained on the study protocol and on recording of data on CRFs prior to

reading images. Determinations made by site radiologists based on DBT and FFDM images collected in this study may be included in the subject's regular medical record.

10. DATA ANALYSIS AND STATISTICS

10.1. Statistical Analysis Methods

10.1.1. Sample Size Justification

The projected sample size is determined by the need to accrue at least 120 cancer cases and 250 non-cancer cases for the overall GE Healthcare SenoClaire® - GE Breast Tomosynthesis (DBT) development program. To achieve these overall accrual targets, the data from this study will be pooled with data from other studies (e.g. ADAPT-SCR and ADAPT-ENRICH).

In this study, for an enrollment of 275 subjects recommended for breast biopsy, it is assumed, based on the GE-190-003 experience, approximately 33% are expected to have a proven cancer and approximately 33% will have a benign lesion. So, at least 90 cancer cases and 90 non-cancer cases are expected to be accrued in this study. Up to 275 subjects referred for breast biopsy (Enrollment ceiling per site will be 165 subjects) will be enrolled from three (3) centers located in the US and Europe (France) until at least 90 histopathology-confirmed cancers have been accrued.

Based on the GE-190-001 experience, for an enrollment of 250 subjects having screening mammography, about 185 (75%) will complete the study with a normal 1-year follow-up. Approximately 2% are expected to have a proven cancer either at screening or during follow-up, which will provide an estimated 6 cancer cases that are expected to be accrued in the ADAPT-SCR study.

In the ADAPT-ENRICH study, for a target enrollment of 90 subjects recommended for breast biopsy, it is assumed, based on the GE-190-003 experience, approximately 33% are expected to have a proven cancer. Thus, at least 30 cancer cases are expected from the ADAPT-ENRICH study.

With the combination of these studies (ADAPT-SCR, ADAPT-BX, and ADAPT-ENRICH), it is expected that at least 120 cancer cases and 250 non-cancer cases will be accrued for the overall GEHC DBT development program. If necessary, data from other sources may also be included to achieve the required number of cancer and non-cancer cases.

The accrued DBT and FFDM images will be used in a blinded image evaluation to analyze the diagnostic performance of SenoClaire® - GE Breast Tomosynthesis (DBT) compared to FFDM through receiver operating characteristic (ROC) analysis, sensitivity, specificity, recall rate, and other analyses.

No statistical analyses are included as part of this study. A descriptive summary will be provided for data collected in this study.

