5.3. Study Endpoints

5.3.1. Primary endpoints

The primary endpoint will be the respective site's diagnosis for each subject of cancer status (positive or negative/benign) based on histology of biopsy/surgical findings and histologic concordance with imaging for benign lesions.

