7.4. Procedures for Enrollment

All subjects must satisfy all the inclusion criteria and none of the exclusion criteria defined in the protocol. Subjects must sign and date the informed consent form prior to completing protocol specific procedures. The Investigator may discuss with the Sponsor any subject who does not strictly meet the inclusion/exclusion criteria but who is thought to be otherwise appropriate for the study; if the Sponsor and Investigator agree that inclusion of the subject would not affect the scientific or ethical aspects of the study, the Sponsor may provide a written exception for the subject. In this case, the details of the exception will be recorded on the Case Report Form (CRF). A subject will be considered enrolled when determined eligible and informed consent is signed, whether or not the subject undergoes study procedures.

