8.3. Biopsy Procedures

Percutaneous and open surgical breast interventions will proceed as per standard of care at the recruiting site. The interpretation of the local pathologist will be recorded on the CRF.

If the subject does not complete the biopsy procedure as scheduled or if the biopsy procedure is not successful or produces indeterminate results that are not able to be resolved by clinically indicated procedures, such as repeat biopsy(ies), the subject will be withdrawn.

For benign/negative histopathology results, the site radiologist will review the subject's imaging and histopathology findings for concordance, per the site's standard of care, and results will be captured on a CRF. Histologic concordance with imaging for negative or benign lesions will be considered truth for non-cancer status. If surgical excision is recommended even after concordance between imaging and histopathology, the resulting histopathology from surgical excision may be collected as part of the study.

Subjects who have negative or benign histology findings that are discordant with imaging shall be followed-up per the site's standard of care. If rebiopsy is recommended, the histology findings and concordance assessment of the rebiopsy will be used to determine the subject's cancer status. If rebiopsy is not recommended or if histopathology remains discordant with imaging findings after rebiopsy, the subject will be withdrawn from the study.

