10.1.2. Study Populations

The *Efficacy Population* will consist of those subjects meeting the study inclusion/exclusion criteria with no protocol violations judged to affect the ability to evaluate the subject whose DBT and FFDM images are diagnostically evaluable, and whose mammography images are available for the independent blinded evaluation regardless of the image quality. Non-available images will include:

- those lost due to corrupted media or inability of site to transport to image review center;
- subjects where no images are acquired.

The Sponsor will make any decisions regarding whether any subjects or any individual values belonging to a subject will be excluded from the evaluations when a protocol violation is considered to have a negative impact on the scientific aspects and interpretation of the study results. The reason(s) for any exclusion(s) will be documented in the study report.

The *Safety Population* will include all subjects enrolled into the study.

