10.3. Handling of Missing Data

There will be no imputation of missing data and collected data will be analyzed as is.

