10.4. Pass/Fail Criteria of the Study

No statistical criteria for success are defined for this accrual study, which will be considered successful if subject number and truth accrual targets are met, without consideration for subsequent analysis results.

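### Does section 10.1.1 leave a third of the 275 women without an outcome that the analysis needs?

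*Combined protocol and SAP*

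**What the plan says.** - **Projection (10.1.1).** For 275 women, based on an earlier sponsor study, "approximately 33% are expected to have a proven cancer and approximately 33% will have a benign lesion". The section concludes that 90 or more of each are expected. It gives no rate for dropout, indeterminate biopsy or discordance.
- **Who is counted (7.4).** A woman is enrolled once she is eligible and has consented, "whether or not the subject undergoes study procedures".
- **Endpoint (5.3.1).** The primary endpoint is the site's "diagnosis for each subject of cancer status (positive or negative/benign) based on histology of biopsy/surgical findings", with imaging concordance added for benign lesions. There are two categories.
- **Truth and withdrawal (8.3).** "Histologic concordance with imaging for negative or benign lesions will be considered truth for non-cancer status". For discordant benign results: "If rebiopsy is not recommended or if histopathology remains discordant with imaging findings after rebiopsy, the subject will be withdrawn from the study". Women whose biopsy is not completed, fails or stays indeterminate are also withdrawn.
- **Populations (10.1.2).** Besides eligibility and the absence of relevant protocol violations, the Efficacy Population requires women "whose DBT and FFDM images are diagnostically evaluable, and whose mammography images are available for the independent blinded evaluation regardless of the image quality". Cancer status is not among the conditions. The Safety Population is everyone enrolled.
- **Missing data (10.3).** "There will be no imputation of missing data and collected data will be analyzed as is".
- **Success (10.4).** The study "will be considered successful if subject number and truth accrual targets are met".

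**The concern.** Every woman in this study has been referred for biopsy, so a reader expects the projected outcomes to cover the cohort. They cover two thirds of it, and the text does not say why. Either the benign share is a cautious minimum and many of the remaining women will also prove benign, or about a third of the cohort is expected to finish without an established status.

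On the second reading the analysis text looks thin. The endpoint has no category for undetermined status. The last paragraph of 8.6.1 refers withdrawn women to the populations in 10.1.2, and 10.1.2 has no rule on withdrawal or missing truth. Read literally, a woman who is imaged and then withdrawn for unresolved discordance meets every condition for the Efficacy Population but has no endpoint value.

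If so, the denominator for cancer status would be undefined. The loss might also be selective, because discordance depends on the lesion and how it looks on imaging. And a success test based on accrual targets would not reveal it.

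**Working it through.** **Inputs.** Enrollment 275; cancer share 33%; benign share 33%; program targets 120 cancers and 250 non-cancers; ADAPT-SCR contribution 6 cancers and 185 women with normal follow-up; ADAPT-ENRICH contribution 30 cancers. All are in 10.1.1.

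**1. The plan's own figures.** 275 × 0.33 = 90.75 for each group, which reproduces the stated 90 and 90.

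**2. The remainder.** 275 − 90.75 − 90.75 = 93.5, or 34%. Reading 33% as one third gives 91.7 in each group and 91.7 left over, so rounding does not close the gap.

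**3. Cancer share by denominator.** Let k be the number of remaining women who enter the denominator as non-cancers. The share is 90.75 / (181.5 + k).

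| k | Cancer share |
|---|---|
| 0 (projected status only) | 50.0% |
| 25 | 43.9% |
| 50 | 39.2% |
| 75 | 35.4% |
| 93.5 (all enrolled) | 33.0% |

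If all the remaining women had cancer, the share would be (90.75 + 93.5) / 275 = 67%. Nothing in the documents points that way.

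**4. Do the program totals need the remaining women?**
- Cancers: 90 + 6 + 30 = 126, against 120. Taking 2% of 250 as 5 rather than the stated 6 gives 125, still above 120.
- Non-cancers: 90 + 185 = 275, against 250, with none counted from ADAPT-ENRICH. This study would have to supply only 250 − 185 = 65.

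The totals hold, as expected values, without any of the 94.

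**5. Where the plan places women without an established status.**
- 8.3 withdraws them; 8.6.1 repeats the rule for discordance.
- 8.6.1 requires the reason for withdrawal on the case report form and a report to the sponsor.
- The end of 8.6.1 counts them as enrolled, and 10.1.2 keeps them in the Safety Population.
- 10.1.3 summarizes enrolled, imaged and withdrawn women overall and by site.
- 10.3 rules out imputation, so a missing status is assigned to neither class.

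**6. Which planned output uses the cancer share?** None. Section 5.1 states that no hypothesis is tested, and 10.1.1 limits the study to a descriptive summary. No section names a cancer proportion or a denominator for one. Enrollment also closes once the required cancers are found (7.1), so any such share would partly reflect the stopping rule.

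**The case for a change.** The best case for a change is that it would be cheap and that the gap is real. The 34% is unexplained. Section 8.6.1 does refer to a section with no applicable rule, and the literal Efficacy Population does admit a woman with images and no truth. Withdrawal for discordance is unlikely to be random. Section 10.4 does not list its truth targets. If 90 non-cancers is one of them, it could be met with heavy loss: at most 275 × 0.67 = 184.25 women could be non-cancers, and losing 94.25 of them (51%) would still leave 90. A few sentences and one table from data already collected would answer all of this.

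The facts stand; the consequence does not. A one-third loss of truth is the less supported reading. The change log in Appendix C (item 60) shows that the benign share was once tied to a normal one-year follow-up, whereas 8.3 now accepts concordant benign histology. That suggests a cautious figure carried over, with some of the remaining women likely to be benign. The point about 10.4 is conditional: the only case count that governs enrollment here is 90 cancers, while 90 non-cancers is an expectation. A category for truth not established would largely repeat withdrawal with its recorded reason. Selective loss would matter mainly for the later blinded read, whose rules are in a separate protocol and cannot be judged from this one.

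**Conclusion.** No change is needed. Section 10.1.1 leaves 34% (about 94 of 275) without a projected outcome, and 10.1.2 is silent on women withdrawn without truth. Both are omissions of detail. No stated figure is wrong: 90.75 supports each 90, and the program totals exceed their targets by 6 cancers and 25 non-cancers. If someone chose to report a cancer share, it could lie between 33% and 50% depending on the denominator, but the plan reports none and tests nothing. An analyst following the text would list women without an established status as withdrawn, with the reason, and leave them out of any tabulation by cancer status.

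This rests on two assumptions: that the contributions projected for ADAPT-SCR and ADAPT-ENRICH are roughly realized, and that ADAPT-BIE sets its own rule for cases without truth. The source of the 33% figures is an earlier study not available here, so which reading of the remainder is right cannot be settled. The conclusion is the same under both.

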
Primary endpoints: The primary endpoint will be the respective site's diagnosis for each subject of cancer status (positive or negative/benign) based on histology of biopsy/surgical findings and histologic concordance with imaging for benign lesions.
 
Characteristic Endpoints: Characteristic endpoints for all subjects will include histology findings and size, lesion type, and other lesion characteristics based on image appearance. Technical characteristics of electronic image data collected from subjects, such as information related to radiation dose, may be extracted and analyzed by the Sponsor for the purposes of this study.
 
Safety endpoint: Device-related adverse events (AEs), serious adverse events (SAEs), and device malfunctions by overall occurrence and imaging modality (DBT and FFDM) that occur during the study will be collected. No other clinical safety assessments will be performed.
	

Sample Size: Up to 275 subjects referred for breast biopsy (Enrollment ceiling per site will be 165 subjects) will be enrolled in this recruitment plan until at least 90 histopathology-confirmed cancers have been accrued. Sample size is determined by the need to accrue at least 120 cancer cases and 250 non-cancer cases for the overall GE Healthcare (GEHC) DBT program (ADAPT-BIE).
	

Research Manager Name: [name] Research Manager – Women's Health
	
Address: [name], US [contact] E-mail: [contact]

Medical Monitor Name: [name] Medical Director, GEHC Quality-Medical Affairs
	
Address: [name], US [contact]

Study Title: Assessment of Diagnostic Accuracy and Performance of Digital Breast Tomosynthesis Compared to Mammography (ADAPT Trial)

Study Number: 124.03-2014-GE-0010

Protocol: 4.0

GE Healthcare

	E-mail: [contact]
--	---

LIST OF ABBREVIATIONS

2-D	Two-dimensional
3-D	Three-dimensional
ACR	American College of Radiology
ACRIN	American College of Radiology In Network
AE	Adverse Event
ALARP	As Low as Reasonably Practicable
ASF	Artifact Spread Function
AUC	Area Under the Curve
BIE	Blinded Image Evaluation
BI-RADS®	Breast Imaging Reporting and Data System
CC	Craniocaudal
CFR	Code of Federal Regulations
CHF	Clinical History File
CRF	Case Report Form
DBT	Digital Breast Tomosynthesis
DCF	Data Clarification Form
DGS	Detection and Guidance Solutions
DMP	Data Management Plan
EC	Ethics Committee

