6.2. Study Timeframe

The study is expected to begin in the fourth quarter of 2014, and last for approximately two years (24 months), or until the target subject population is enrolled or the Sponsor otherwise indicates in writing that enrollment should be terminated. The end of the study shall be defined as the date when the last subject undergoes biopsy procedures and concordance is established, if applicable. Subject participation will be from the point of enrollment until truth determination of cancer status. The Investigator shall not begin the study until the applicable EC/IRB and necessary regulatory authority (when required) approval have been obtained.

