7. STUDY SUBJECTS

7.1. Number of Subjects

Up to 275 subjects referred for breast biopsy (Enrollment ceiling per site will be 165 subjects) will be enrolled from three (3) centers located in the US and Europe (France) until at least 90 histopathology-confirmed cancers have been accrued. Enrollment will be closed once the required number of cancers has been histologically identified. Data will be pooled with other

sources to achieve the target number of positive and negative cancer cases, as described in Section 10.1.1 Sample Size Justification.

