33.	Section 6.1.1. Study Type	
This study (ADAPT-BX) is an open-label, multi-center, within-subject crossover, prospective, clinical research study, collecting images and associated data from bi-lateral two-view DBT and FFDM exams conducted with GE systems comparing DBT and FFDM in the detection of breast cancer.
 
Figure 1. Study Design and Procedures
 <pre> graph TD A[Histopathology] -- Benign/Negative --> B[Image & Histopathology Concordance Review**] B -- Concordant --> C[1 yr F/U (10-16 mo) FFDM AND applicable Standard of Care Follow-up] </pre> 
** In the event of discordant histopathology and imaging findings, rebiopsy and resulting histopathology results will be acquired to establish concordance. If no rebiopsy or histopathology occurs, or if histopathology remains discordant with imaging findings, the subject will be withdrawn from the study.
	
Revised to represent this study's objective and to clarify that the comparison of the two modalities will be conducted under a separate protocol.
 
Figure 1 updated to include assessment and documentation of concordance for negative/benign cases. Added language describing the process for discordance.

34.	Section 6.3. Controls and Minimization of Bias	
a. Selection bias in allocating subjects to interventional groups will be limited by attempting to enroll consecutively eligible subjects. To reduce bias introduced from this study by subjects who are expected to be referred for biopsy primarily based on FFDM screening, other sources (e.g. ADAPT-ENRICH) may be pooled to include cancer cases reaching biopsy through a DBT screening program.
	
Clarified that the majority of subjects are expected to be referred from an FFDM screening population.

35.	Section 7.1. Number of Subjects	
Up to 275 subjects referred for breast biopsy (Enrollment ceiling per site will be 165 subjects) will be enrolled from three two (3 2) centers located in the US and Europe (France) until at least 90 (max. 95) histopathology-confirmed cancers have been accrued.
	
Updated number of participating sites.
 
Clarified the minimum accrual target for histopathology-confirmed cancers and removed the maximum limit to allow for meeting the target.

Item	Section	Revision or Clarification	Justification																																												

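### Section 10.1.1 presents 90 cancers as a minimum, but 90 is about the mean at the 275 ceiling, and the plan's own 33% rate reaches it only about 56% of the time

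*Combined protocol and SAP*

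**What the plan says.** Section 10.1.1 (Sample Size Justification) takes an enrolment of 275 women recommended for biopsy and a cancer proportion of approximately 33%, drawn from a previous sponsor study, and concludes: "So, at least 90 cancer cases and 90 non-cancer cases are expected to be accrued in this study".

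The same 90 governs enrolment. The synopsis says that up to 275 subjects "will be enrolled in this recruitment plan until at least 90 histopathology-confirmed cancers have been accrued". Section 7.1 repeats the cap and adds: "Enrollment will be closed once the required number of cancers has been histologically identified".

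Section 10.4 sets no statistical criterion for this accrual study, "which will be considered successful if subject number and truth accrual targets are met". It does not list those targets. For the pooled program targets of 120 cancers and 250 non-cancers, Section 10.1.1 adds: "If necessary, data from other sources may also be included to achieve the required number of cancer and non-cancer cases".

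**The concern.** In one section, 90 is both what 275 women are expected to yield and the number at which enrolment may stop. A reader who sees a lower bound attached to an expectation will take 90 as a cautious figure with margin behind it. Appendix B encourages this reading when it explains the present wording of 7.1: "Clarified the minimum accrual target for histopathology-confirmed cancers and removed the maximum limit to allow for meeting the target".

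If 90 is instead close to the mean, a hard cap of 275 leaves almost no margin. The study could then follow its plan exactly, with its cancer-rate assumption correct, and still end below 90 nearly as often as not. The plan does not state this risk. What is at stake is an accurate statement of the study's yield for those who rely on 90 when planning the pooled data set.

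**Working it through.** **Inputs.** Cap of 275 (synopsis, 7.1, 10.1.1). Cancer proportion p of approximately 33% (10.1.1), taken as 0.33, with 0.325 to 0.335 as the range if it is rounded to a whole percent, and 1/3 as a variant. Required cancers: 90. The site ceiling of 165 does not bind, since 3 × 165 = 495.

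**Step 1: the plan's own figure.** 275 × 0.33 = 90.75 (275/3 = 91.7). The stated 90 is reproduced as an expectation at full enrolment.

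**Step 2: spread around it.** Let X be the number of cancers among 275 women, X ~ Binomial(275, 0.33). SD = √(275 × 0.33 × 0.67) = 7.80. The median is 91, and the 2.5th and 97.5th percentiles are 76 and 106.

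**Step 3: chance of reaching 90 within the cap.** The 90th cancer occurs by subject 275 exactly when X ≥ 90, so the chance is the binomial tail P(X ≥ 90):

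| Cancer proportion | Mean at 275 | P(X ≥ 90) |
|---|---|---|
| 0.325 | 89.4 | 0.491 |
| 0.33 | 90.75 | 0.561 |
| 1/3 | 91.7 | 0.607 |
| 0.335 | 92.1 | 0.629 |

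At 33% the chance of falling short is 1 − 0.561 = 0.439.

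**Step 4: size of a miss.** At 33%, given X < 90, the mean shortfall is 6.25 and the median count is 85.

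**Step 5: what would serve as a floor.** At 33% and 275 women, P(X ≥ 84) = 0.82 and P(X ≥ 85) = 0.79; P(X ≥ 81) = 0.91 and P(X ≥ 82) = 0.88. So 84 is the largest count supported with at least 80% probability, and 81 with at least 90%.

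**Step 6: effect of closing at 90.** With an exact stop at the 90th cancer the yield is min(X, 90). Its expectation is 90 − 0.439 × 6.25 = 87.3 (86.6 at 0.325, 87.8 at 0.335). In practice some women will be enrolled while earlier biopsies are still being read. If that number is 20 or 30 (an assumption; the plan gives none), simulation with the cap at 275 gives 89.8 or 90.3. With no early stop the expectation is 90.75. Closing at 90 removes only the overshoot. It does not cause a miss.

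**The case against.** The strongest reply is that the sentence in 10.1.1 is true. It is conditional on 275 enrolled, it speaks of an expectation, and 90.75 exceeds 90. That stands: there is no arithmetic error, and nothing in the sentence promises a floor in so many words. What remains is that a lower bound is attached to a mean, in a section where the same number is the enrolment requirement, with no range or probability beside it.

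The second reply is that the consequence is limited. Section 5.1 says that no hypothesis is tested here. The sample size is driven by the pooled targets, and on the plan's own counts the pool is 90 + 30 + 6 = 126 cancers. If this study yields 85, the median count given a miss, the sum is 85 + 30 + 6 = 121, still above 120, and other sources may be added. This also stands. It limits the point to this study's stated yield.

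A third reply is that an exact probability is too precise for an input given as approximately 33% from a study not in the documents. That is fair, and it is a reason to print a rounded statement in the protocol.

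Three stronger readings may tempt a reader:

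- *The study has a 44% chance of failing its success criterion.* Section 10.4 does not say which truth accrual targets it means. Section 10.1.1 also uses the language of accrual targets for the program totals of 120 and 250. The 44% applies to 10.4 only if 90 is the target meant.
- *Closing at 90 conflicts with a subject-number target of 275.* Enrolment statements in the synopsis, 7.1 and 10.1.1 give 275 as a maximum, so no required number exists for the closing rule to defeat.
- *The companion figures are also wrong.* 33% of 90 is 29.7 against the stated 30, and 2% of 250 is 5 against the stated 6. Both rates are given as approximate, and the differences lie within that rounding.

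**Conclusion.** The point holds as one about how the yield is stated. At the plan's rate, 90 cancers is about the mean for 275 women and is reached within the cap about 56% of the time, or 49% to 63% across the rounding range. The remaining 44% or so of outcomes fall short by about 6 on average. The expected yield under the enrolment rule runs from about 87 with an exact stop to about 90 with a modest lag before closure.

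These figures assume independent subjects, one cancer rate across the three centers, and a 33% that is already net of withdrawals. Variation between sites or uncertainty in the earlier study's rate would widen the spread.

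A reader might infer that the reader study loses power. The documents do not show this: the ADAPT-BIE protocol is not among them, and the pooled totals have some slack and a provision for other sources.

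**What to change.** In Section 10.1.1, replace the statement of the cancer yield with wording such as: *about 90 cancer cases are expected at the 275 ceiling (95% range about 76 to 106 at 33%; reaching 90 within the ceiling is only somewhat more likely than not, roughly 50% to 60%)*. The 90 non-cancer cases are not in question and can stay.

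Leave the synopsis and Section 7.1 as they are, since they state an enrolment rule and not an expectation. No enrolment is added, and neither the cap nor the closing rule changes. Naming in Section 10.4 the targets that decide success is an optional clarification.

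The cost is one sentence of protocol text and a slightly less favourable stated yield.
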